6. STUDY PROCEDURES

Potential subjects will have the study risks and possible benefits explained to them, the ICF reviewed with them, and all questions answered for them. Subjects will undergo procedures specific to study qualification (Section 6.1) only after the ICF is signed by the subject/or the subject's legal representative, and age appropriate assent obtained from subjects capable of doing so. Subjects who complete the screening period and are determined to be eligible for study participation per the inclusion and exclusion criteria will be randomized in a 1:1 ratio to either the edoxaban-treatment arm or the SOC-treatment arm.

All subjects will undergo safety objectives evaluations at the EOT at Month 3 and at 30-days thereafter. Subjects who participate in the Extension Period will undergo safety objectives evaluations (recurrent VTE events, bleeding events, or any other AEs) at Months 6, 9, and 12, and 30-days after cessation of treatment if treatment up to 12 months is required.

The Schedule of Events for this study is provided in Appendix 17.1.

6.1. Screening: Study Qualification (At least Day -5 to -1, Visit 1)

Any protocol-specified study qualification procedures/tests not already done as part of routine care will be conducted only after the subject signs the ICF and before randomization.

Note: A newly diagnosed VTE or diagnostic workup may have been performed prior to identifying the subject for the study and signing the consent.

Prior to signing the ICF, potential subjects and their parent(s)/guardian(s) will have the study risks and benefits explained to them, the associated ICF and assent form if applicable will be reviewed, and all questions answered for them. Written informed consent must be signed by the parent(s)/guardian(s) of all subjects, and assent obtained from the child, when and where applicable, prior to entry into the study.

- It is anticipated that some subjects will have had some of the study qualification procedures done as part of routine care outside the auspices of this study (for example, diagnostic work-up and associated care for index VTE). As long as these procedures were done for the newly diagnosed index VTE before randomization, they may be used to complete the Screening eCRF.
- A Screening eCRF must be completed for every subject with a signed ICF. Any protocol-specified study qualification procedures/tests not already done as part of routine care will need to be conducted after the parent(s)/guardian(s) signs the ICF and before randomization.
- Register the subject for screening within IXRS Screening Visit and subject number will be provided.
- For subjects who did not have any protocol-specified screening procedures done as part of routine care for the newly diagnosed index VTE before randomization, the following study qualification procedures must be completed to ensure that the subject is eligible for the study.
 - Review inclusion/exclusion criteria

- VTE Radiologic Image: After index VTE diagnosis is confirmed through the appropriate imaging techniques (see Section 7.1) send the results to the Clinical Evaluation Committee for adjudication
- Record demographic information (date of birth/age, sex, ethnicity, and race)
- Record medical/surgical history,
- Record prior medication (up to 30 days prior to screening)
- Perform physical examination including:
 - Vital signs (BP, heart rate, and body temperature after resting in a sitting or supine position [Note: the appropriate cuff size base on arm circumference will be used.] see Section 9.9)
 - Height and body weight (may be performed by an Investigator or other healthcare provider designated by the Investigator).
- Assess the subject for active bleeding, high risk for bleeding and any other contraindications for treatment with LMWH, or UFH, SP anti-FXa, VKAs or NOACs.
- INR assessment and aPTT measurement to monitor coagulation for all subjects
- Ensure that the subject qualifies with regard to the following laboratory tests for exclusion criteria:
 - Liver function assessments (ALT, AST, TBL, ALP)
 - Serum chemistry panel, Serum creatinine, and eGFR
 - Hematology
 - Urinalysis
 - Urine pregnancy test (for post-menarchal females)
- Samples taken as part of routine care outside study auspices may be analyzed by local laboratories and the results used to qualify the subject provided the tests (INR, aPTT, ALT, TBL, eGFR and platelets) were performed for the newly diagnosed index VTE before randomization. Alternatively, the central laboratory may be used for the above study qualification laboratory tests. If central laboratory is also used at the same visit with a resulting discrepancy for exclusion criteria, the local laboratory result will still be used to qualify the subject.
- Review concomitant medications for assessment of exclusion criteria.
- Assess for and record AEs and concomitant medications.

Full documentation for the above qualifying procedures and related results are required even if local laboratory results were used to qualify the subject.

6.1.1. Screening Period Prior to Randomization

Initial treatment using LMWH or SP Xa inhibitor or UFH for index VTE prior to randomization must be within the range of 5 to 15 days and up to 20 days with Sponsor approval. In addition, prior to being randomized to edoxaban or SOC, subjects initially treated with VKA are recommended to have an INR ≤ 2.5 .

6.2. Randomization (Day 1, Visit 2)

If all procedures and tests done before randomization confirm the subject's eligibility (Section 4.1) for the study, then the IXRS will be contacted to randomize the subject. Randomization may occur in IXRS the day prior to dosing for clinical logistics. The following activities should be done at the time of randomization:

- Record any prior medications used since the last visit.
- Record any AEs since screening visit.
- Urine pregnancy test (for post-menarchal females)
- Dispense study drug and record amount (number of tablets/bottles) dispensed. Locally sourced SOC study therapy will need to be supported by a prescription identifying the type of SOC to be provided;
- Explain the study medications and the proper daily dosing to the parent/guardian and subject (if applicable) using the study medication dosing calendar, and confirm that the subject understands the proper daily dosing of study medication.
- Instruct subject to bring all medications including study drug packaging and bottles to each visit.

Provide parent(s)/legal guardian(s) or legally acceptable representative parent(s)/guardian(s) and subject (if applicable) information with detailing symptoms suggestive of recurrent VTE and bleeding. Parent(s)/guardian(s)/subject will be asked to immediately contact the Investigator if these symptoms occur.

The following information will be provided to the parent/subject (information booklet):

- The local medical contact person and emergency telephone number
- The visit schedule provided by the IXRS (fax or email with dates of telephone and/or hospital visits)
- How to recognize and report signs and symptoms of possible recurrent symptomatic PE/DVT or bleeding (see Section 7.1 and Section 9.2.1).
- Instructions to keep empty medication packages
- How to use the study medications
- The scheduled dates of blood collections for the next INR control if VKA is dispensed
- Provide subjects with a subject identification safety card and a prohibited medication card

The Investigator will use discretion to decide when and how often to repeat INR or anti-FXa levels or aPTT measurements or fondaparinux levels. These measurements will be taken in the clinic, or alternatively, optional site-specific local laboratory (Appendix 17.2).

All suspected VTE and bleeding endpoints as well as hepatic abnormalities identified by the Investigator will be adjudicated by the CEC. Adjudication packages will contain copies of images (or films) of appropriate diagnostic tests, clinic notes, laboratory tests, discharge summaries, autopsy reports, etc. used in the subject work-up following a suspected event.

Investigators will maintain a confidential subject identification code list of names of all subjects randomized to study to allow the Investigator to reveal the identity of any subject when necessary.

6.3. Main Treatment Period

The Main Treatment Period is defined as the time from randomization until the end of Month 3 of treatment. The Main Treatment Period for subjects <6 months old (Cohort 5) is defined as the time from randomization until the end of anticoagulant therapy for at least 6 to 12 weeks.

6.3.1. Subjects randomized to the edoxaban treatment arm:

For the approximately first 12 subjects of each age cohort randomized in edoxaban-treatment arm, two blood samples will be collected on Day 5+3 days. Dosing on Day 5 will be done in the study center. Note: If the subject did not initiate dosing of edoxaban on the randomization day (Day 1), the Day 5 PK/PD assessment should be scheduled when the actual Day 5 dose is taken.

Edoxaban will be started orally at the age/weight/renal function appropriate dose (depending on the results of the ongoing U157 study) for the treatment period. The study will start enrollment from older to younger children as data from the single dose PK, PD study become available for each age cohort (Study U157). After Month 3, dispense may be provided for a 3-month period to align with the visit schedule based on approval of the Sponsor.

For subjects in Cohort 5, the Principal Investigator (PI) may use medical discretion and clinical judgment to determine the duration of anticoagulation treatment. For these subjects, the intended duration of treatment should be at least 6 to 12 weeks. If 6 weeks' duration is chosen, a radiologic VTE image will be taken and will be assessed by the PI to determine if an additional 6 weeks of treatment is required. After 12 weeks, an additional radiologic VTE image will be taken by the PI to assess whether the subject should continue on treatment into the extension.

Approximately 12 subjects from each age cohort (total of approximately 53 to 60 subjects) will participate in the multiple-dose PK/PD assessment (subject number is determined by evaluable blood specimens demonstrating edoxaban exposure). For the youngest Cohort 5 (birth to <6 months), 5 to 12 subjects on edoxaban will be enrolled.

- Ages 12 to <18 years (N≈12)
- Ages 6 to <12 years (N≈12)
- Ages 2 to <6 years (N≈12)
- Ages 6 months to <2 years (N≈12)
- Ages birth to <6 months (N≈5-12)

6.3.1.1. Study Day 5 (+3 days) for Subjects Randomized to Edoxaban Only (Visit 2a)

Subjects participating in the Day 5 edoxaban evaluation will need to bring their edoxaban treatment (wallet card or bottle of granules) to the clinic for dosing that day. A witness should observe the edoxaban dose taken on Day 5 after the pre-dose blood specimen is collected.

Each subject included in the multiple-dose PK/PD assessment will have a laboratory developed test (LDT) PK assay performed for edoxaban exposure verification. The first approximately 12 subjects participating in PK/PD assessment should be fasted one hour prior to the uptake of edoxaban dose and a maximum of 2 hours after taking edoxaban dose. If this is not feasible because of the subject's age or other needs, milk, or an equivalent substitute liquid (but not fruit juices or caffeinated drinks), will be allowed until 1 hour before and starting at 1 hour post-dose.

In preparation for the Study Day 5 visit, subjects will be instructed to do the following:

- Record date/time of the last 2 study drug doses taken before the Day 5 visit
- Record date/time of the last meal taken before the Day 5 visit
- Record time of study drug dose taken on visit day

The PK sampling windows (hours) on the day of the fifth dose of edoxaban (Day 5+3 days) is planned to occur as follows:

- PK Pre-dose sample for all participating subjects.
- PK Post-dose sample can be taken at either:
 - any time between 1.0 to 3 hours post-dose
 - any time between 5 to 8 hours post-dose
- The PD sampling times on Day 5 for measurement of PT, aPTT and anti-FXa, will be the same time as the PK samples.
- An edoxaban PK analysis will be performed on Day 5 subjects in U312 study. If the analysis of the subjects confirms the edoxaban exposure predictions and based on emerging safety, the expanded enrollment in the same age cohort will be allowed to start. A notification will be sent to all Investigators that expansion of the age cohort is permitted after the PK analysis. In addition, a notification to the investigator will indicate that Day 5 PK/PD edoxaban exposure evaluation will no longer be necessary for future subjects randomized to edoxaban in the corresponding age cohort.
- For subjects in Cohort 5, specifically those ≤ 28 days old, a renal function test (RFT) will be performed on or around Day 5 (at the same time of PK sampling).

Enrollment in the next younger age cohorts in U312 study will begin upon the availability of:

- PK analysis performed on Day 5 participant subjects in the prior older age cohort in U312
- Safety data analysis on Day 5 subjects in the prior older age cohort in U312
- PK analysis of the subjects in the next younger age cohort in U157.

- Safety data analysis on the subjects of the next younger age cohort in U157.

PK and safety data will be reviewed by an IDMC, (Section 15.9) who will approve the start of the next younger age cohort.

In each age cohort, if the estimated median AUC based on the observed PK data in participating subjects in the Day 5 PK assessment is less than 1.5-fold the median AUC from the simulated subject population profiles (over-exposure and under-exposure), the enrollment of subjects in the corresponding age cohort will continue and enrollment in the next younger age cohort can begin.

The following will be performed at this visit:

- Review dosing instructions
- Safety review for AEs/SAEs
- Review for endpoint events (VTE, bleeding)

The Investigator will use discretion to decide when and how often to repeat INR or anti-FXa levels or aPTT measurements or fondaparinux levels. These measurements will be taken in the clinic, or alternatively, optional site-specific local laboratory (Appendix 17.2).

6.3.2. Subjects randomized to the SOC treatment arm:

Standard of Care treatment will be dispensed to the subject on a monthly visit schedule. After Month 3, dispense may be provided for a 3-month period to align with the visit schedule based on approval of the Sponsor. SOC will be provided by the Investigator. Subject will be treated with LMWH, VKA, or SP Xa inhibitors according to the site SOC treatment (Section 5.1.1.2). However, if there are regulatory or site hurdles providing the SOC, the Sponsor will provide SOC as enoxaparin or fondaparinux or warfarin (see below).

If Investigators choose to use the SOC supplied by the Sponsor, the subject will be treated as follows:

- Enoxaparin – Subjects will be treated with enoxaparin alone or can be switched to warfarin anytime during the study treatment period.
- Fondaparinux – Subjects will be treated with fondaparinux alone or can be switched to warfarin anytime during the study treatment period.
- For subjects in whom clinicians prescribe warfarin, this will be started on Day 1. Heparin (exoxaparin or fondaparinux or UFH depending on the therapy received during pre-randomization period) will be discontinued when INR ≥ 2.0 and ≤ 3.0 for 2 consecutive measurements obtained at least 24 to 48 hours apart. The subject will continue warfarin for the remainder of the study treatment period.

The Investigator will use discretion to decide when and how often to repeat INR or anti-FXa levels or aPTT measurements or fondaparinux levels. These measurements will be taken in the clinic, or alternatively, optional site-specific local laboratory (Appendix 17.2).

6.3.3. Monthly Visits (Months 1 and 2; Visits 3 and 4) for both arms:

Starting with the Month 1 visit, subjects will return to the clinic every 30 days \pm 5 days (depending on the visit, see Schedule of Events in Appendix 17.1) until the Month 3 visit (Visit 5) or study withdrawal. For Cohort 5, the subjects may return to the clinic earlier after the first month, depending on the duration of the therapy (at least 6 to 12 weeks) and imaging at 6 weeks for thrombus resolution.

During study drug interruptions and after study drug discontinuation, subjects will be followed for efficacy and safety endpoints and SAEs until the Month 3 visit (Visit 5) or earlier in Cohort 5 subjects (6-12 weeks). A 30 day Follow-Up Visit (Visit 9) for safety assessment is required after the Month 3 visit (for Cohort 5, the intended duration of treatment is 6 to 12 weeks).

At these monthly on-site visits, anti-FXa levels assessments and aPTT measurements will be performed for the subjects on SOC with LMWH or SP Xa inhibitor, fondaparinux levels if applicable, and INR assessments will be performed for the subject on SOC with VKA. Additional interim visits may be scheduled, at the Investigator's discretion, for anti-FXa levels/INR monitoring.

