3. STUDY DESIGN

3.1. Overall Design

This is an event driven Phase 3, prospective, randomized, open-label, blinded endpoint evaluation (PROBE) parallel group study in subjects with confirmed venous thromboembolism (VTE). A schematic representation of the study design is provided in [Figure 3.1](#). The parallel enrollment strategy schema in U157, U312 and between U157 and U312 is provided in [Figure 3.2](#).

Figure 3.1: Study Design

[figure not shown]
[figure not shown]

Figure 3.2: Enrollment Strategy Schema in U157, U312 and Between U157 and U312 Study

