	
• Spiral CT pulmonary angiography (CTPA)• Magnetic resonance pulmonary angiography (MRPA) 
Alternative imaging techniques:
 
• Cardiac angiography• Conventional pulmonary angiography• echocardiography
Sinovenous thrombosis	
• Brain MRI, including T2 imaging and MRI with venography (MRV)• Pre and post-contrast CT scan with venography (CTV) 
Alternative imaging techniques:
 
• Doppler flow US; if fontanelle open
Renal Vein thrombosis	
• US
Splanchnic and hepatic veins and vena cava	
• Doppler/US• CT/Scan

In certain cases, the use of 2 techniques may be required to objectively confirm the diagnosis of recurrent VTE. Further recommendations will be provided in the imaging manual but will be left for Investigator's discretion.

Diagnosis of fatal VTE is based on 1 or more of the following:

- Objective diagnostic testing
- Autopsy
- Death which cannot be attributed to a documented cause and for which VTE cannot be ruled out.

Thrombotic burden will be assessed by comparison of the diagnostic method used at baseline and at Month 3 \pm 5 days (for Cohort 5, at 6 to 12 weeks \pm 5 days) in the absence of symptomatic recurrent VTE. Hence, the same imaging technique that is used at the enrollment of the subject into the study will be required to be used at the end of the observational period \pm 3 days. A thrombotic burden endpoint will be registered if there is no regression of the thrombus size or extension of the thrombus at Month 3 visit \pm 3 days (for Cohort 5, at 6 to 12 weeks \pm 3 days) after randomization.

Additionally, thrombotic burden will be assessed at Month 12 \pm 5 days / Discontinuation Visit, for those subjects who participate in the Extension Period.

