ⁿ For subjects in Cohort 5, a radiologic VTE image will be taken at the end of the intended treatment period (at least 6 to 12 weeks) or at the discontinuation visit if anticoagulant treatment is received for <3 months.

^o Renal function test should be performed on or around Day 5 visit (at the same time of PK sampling).

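### In Cohort 5 the timing of the thrombotic-burden scan follows a treatment duration chosen by the open-label investigator, and the plan does not say which scan counts when there are two

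*Combined protocol and SAP*

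**What the plan says.** The trial is a "randomized, open-label, blinded endpoint evaluation (PROBE) parallel group study" (section 3.1), and section 5.1.3 lists blinding as not applicable. The investigator therefore knows the arm; only endpoint adjudication is blinded.

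For Cohort 5, section 6.3.1 states that "the Principal Investigator (PI) may use medical discretion and clinical judgment to determine the duration of anticoagulation treatment". When 6 weeks is the chosen duration, "a radiologic VTE image will be taken and will be assessed by the PI to determine if an additional 6 weeks of treatment is required". A second scan is then described, after 12 weeks, from which the investigator judges whether treatment goes on into the extension period.

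The endpoint follows this flexible schedule:

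- Section 7.1 registers a burden event when the thrombus has not regressed or has extended. For Cohort 5 this is read at 6 to 12 weeks after randomization, where the other cohorts are read at Month 3.
- Footnote n of Table 17.1 ties the Cohort 5 image to the end of treatment: "at the end of the intended treatment period (at least 6 to 12 weeks) or at the discontinuation visit", the latter for infants treated for less than 3 months.
- Section 6.3.3, which covers both arms, makes the Cohort 5 return visit depend on the duration of therapy and on what the 6-week imaging shows.

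The primary analysis (section 11.4.1.1) uses time to first event and censors at 3 months + 3 days or at the last complete assessment. It has no Cohort 5 rule. Section 15.10 names the baseline, Month 3 and Month 12/Discontinuation images for the committee radiologist, but no 6-week image.

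**The concern.** An endpoint that is read from a scan needs a scan date that does not depend on the outcome or on knowledge of the arm. Here the date is the end of a treatment course whose length the unblinded investigator chooses and, on the 6-week option, may extend after seeing a scan. Dependence on the scan result is written into the rule. Dependence on the arm is not prescribed, but the open label makes it possible.

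If the two arms are handled differently, their recorded failure rates can differ with no difference in drug effect. Stratifying by age does not prevent this, because the extension decision comes after randomization and nothing requires the initial duration to be fixed before it. Blinded adjudication protects the reading of an image, not the choice of which day the image is taken.

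The 6-week scan rule also appears only in the edoxaban section (6.3.1). The SOC section (6.3.2) has no counterpart, so it is not stated plainly that both arms share one imaging schedule.

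**Working it through.** **The plan's own figure.** Schoenfeld's formula with HR 0.76, margin 1.5 and two-sided alpha 0.05 gives (1.960 + 0.842)² / (0.25 × [ln(1.5/0.76)]²) = 67.9, so 68 events; power at 68 events is 0.800. With 28% in the control arm, N = 68/0.2464 = 276 if the 24% reduction applies to the risk (21.28%), or 68/0.2505 = 271 if it applies to the hazard (22.09%). The plan's 68 and 274 are reproduced. Nothing below changes them.

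**Which scan counts?** Two readings are open.

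- *Later scan.* Section 15.10 names the Month 3 image and no 6-week image, and footnote n points to the end of treatment. An infant with no regression at week 6 is then a failure if treatment stops, but is read again at week 12 if treatment is extended.
- *First scan.* Section 11.4.1.1 uses time to first event, and week 6 lies inside the window of section 7.1. A scan without regression at week 6 is then already an event, whatever follows.

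**Inputs.** Week-6 failure (no regression, or extension) p = 18%. Section 1.1 quotes 18% for infants in one case series, but over follow-up of 5 days to 4.2 years, so its use at week 6 is an assumption. The share of failures extended (f) and the share of those regressing by week 12 (r) are not in the documents and are assumed. The true HR is set to 1.

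**Later scan counts.** Recorded failure = p(1 − f·r), and HR = ln(1 − edoxaban failure) / ln(1 − SOC failure).

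| f edoxaban / SOC | r | Failure edoxaban / SOC | Apparent HR |
|---|---|---|---|
| 0.8 / 0.4 | 0.5 | 10.8% / 14.4% | 0.74 |
| 0.8 / 0.4 | 0.3 | 13.7% / 15.8% | 0.85 |
| 1.0 / 0 | 0.5 | 9.0% / 18.0% | 0.48 |

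The direction reverses if SOC infants are extended more often.

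**First scan counts.** Let s be the share for whom 6 weeks is chosen; the rest are first read at 12 weeks. Recorded failure = p·s + p(1 − s)(1 − r). With r = 0.5, s = 0.2 gives 0.036 + 0.072 = 10.8%, and s = 0.6 gives 0.108 + 0.036 = 14.4%. The same distortion arises from the first choice of duration.

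**Effect on the whole trial.** Sections 6.3.1 and 8 give 5 to 12 edoxaban infants, for the PK/PD assessment. Taking this as the cohort size with 1:1 allocation gives 10/274 = 3.6% to 24/274 = 8.8% of subjects.

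- Main scenario: difference 3.6 points; 0.036 × 5 = 0.18 to 0.036 × 12 = 0.43 events. With 28% failing in the other cohorts, the overall risk ratio is 0.995 to 0.988.
- 100% versus 0% extended, 12 per arm: 0.09 × 12 = 1.08 events.
- Harsher assumptions (p = 50%, r = 0.6, 100% versus 0%, 12 per arm): failure 20% versus 50%, 0.30 × 12 = 3.6 events, overall ratio 0.912.

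With SE = 2/√68, the approximate one-sided error at the margin is Φ(−1.96 − ln(ratio)/SE). It is 0.026 to 0.028 in the main scenario and 0.057 in the harshest case, against 0.025 planned.

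**The case against.** The strongest reply is that time to first event settles the matter: a failed 6-week scan is an event and extension cannot erase it. A reader might infer the opposite, that a good week-12 scan replaces a failed week-6 scan. The documents establish neither. The first-event reading would remove the bias from extension, but not the bias from the initial choice between 6 and 12 weeks.

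Other stronger readings also fail:

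- *Every Cohort 5 infant has a 6-week scan that decides the next step.* Section 6.3.1 applies this only where 6 weeks was chosen.
- *Any thrombus still visible at week 6 is a failure.* Section 7.1 requires no regression or extension, so partial regression is not an event. The 6-week imaging in section 6.3.3 looks at resolution, a different threshold.
- *The arms are scanned on different schedules.* The placement of the rule allows that inference, but section 6.3.3 covers both arms and footnote n is not limited to one. The text is unclear rather than unequal.
- *No document fixes the scan.* Section 15.10 leaves the images to be adjudicated to the committee's charter. What can be said is that the text in hand does not fix it.

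Section 6.3.4 gives all randomized subjects, including those off treatment, an assessment at Month 3. That would fix the date, but its own heading, sections 3.2 and 6.3.3 and footnote n allow an earlier assessment in Cohort 5.

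It is also fair to say that the plan specifies no separate efficacy comparison in Cohort 5 (age is only a covariate), and that the extension and regression shares are assumed.

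**Conclusion.** The concern holds as a weakness in how the Cohort 5 endpoint is timed. Under either reading of which scan counts, assessment time depends on an unblinded choice that is not fixed before randomization; if the later scan counts, it depends on the outcome as well. Any descriptive comparison in infants could be seriously distorted: the illustrated HR runs from 0.85 to 0.48 for equal arms, or the other way if SOC is extended more.

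A reader might infer that the main non-inferiority conclusion is in doubt. The figures do not support that. At 5 to 12 infants per arm the main scenario moves about 0.2 to 0.4 events, and about one event is reached only with 100% versus 0% extension and 12 per arm. Moving several events takes a much higher assumed failure rate together with complete separation of the arms. The documents do not cap Cohort 5, so a larger cohort would scale these figures up. This is an inexpensive improvement that should be made, not a flaw that invalidates the design.

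**What to change.** 1. Record the intended Cohort 5 duration (6 or 12 weeks) in IXRS before randomization, in both arms.
2. In sections 7.1 and 11.4.1.1, define the primary burden endpoint for Cohort 5 as the blinded committee's reading of the scan at that declared time, whatever extension follows. Later scans go to the secondary analysis.
3. For an infant who stops before the declared time, use the scan at the declared-time visit; section 6.3.4 already provides an end-of-period assessment after discontinuation. Use the discontinuation scan only if that one is missing.
4. State that the imaging schedule is the same in both arms.
5. Add two sensitivity analyses: one that counts the first follow-up scan, and one that excludes Cohort 5.
6. Reconcile sections 6.3.1 to 6.3.4, 7.1, 11.4.1.1 and 15.10 with footnote n of Table 17.1.

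Treatment duration and any extension remain the investigator's decision. The cost is one IXRS field, edits in several sections, and possibly a scan at the declared time for infants who stop early. The 68 events and 274 subjects do not change.
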